16.8 APPENDIX H: ORAL MEDICATION DIARY FOR SELINEXOR – WEEKLY

Today's Date _____

Patient Name _____ (*initials acceptable for patient's name*)

Patient Study ID _____

Please bring your pill bottle and this form to your physician when you go for your next appointment.
This is required for study compliance.

INSTRUCTIONS TO THE PATIENT:

1. Complete one form for each cycle (14 days).
2. You will take selinexor tablets on the second day of radiation and by mouth once a week.
Please ask your doctor what dose you will be getting and how often you will get it.
3. Record the date, the number of tablets you took, and when you took them.
4. If you have any comments or notice any side effects, please record them in the Comments column.

| Date | Week/Day | Selinexor | Comments | |
|------|----------|-----------|----------|--|
| | | | | |
| | W1 D2 | | | |
| | W2 D2 | | | |
| | W3 D2 | | | |
| | W4 D2 | | | |
| | W5 D2 | | | |

Patient's Signature: _____ Date: _____

Study Team will complete this section:

1. Date patient started protocol treatment _____
2. Date patient was removed from study _____
3. Patient's planned daily dose _____
4. Total number of pills taken this month _____

Physician/Nurse Practitioner/Nurse's Signature: _____

16.9 APPENDIX I: ORAL MEDICATION DIARY FOR SELINEXOR – TWICE WEEKLY

Today's Date _____

Patient Name _____ (*initials acceptable for patient's name*)

Patient Study ID _____

Please bring your pill bottle and this form to your physician when you go for your next appointment. ***This is required for study compliance.***

INSTRUCTIONS TO THE PATIENT:

1. Complete one form for each cycle (14 days).
2. You will take selinexor tablets on the first and fourth day of radiation. Please ask your doctor what dose you will be getting and how often you will get it.
3. Record the date, the number of tablets you took, and when you took them.
4. If you have any comments or notice any side effects, please record them in the Comments column.

| Date | Week/Day | Selinexor | Comments |
|------|----------|-----------|--|
| | W1 D1 | | |
| | W1 D4 | | |
| | W2 D1 | | |
| | W2 D4 | | |
| | W3 D1 | | |
| | W3 D4 | | |
| | W4 D1 | | |
| | W4 D4 | | |
| | W5 D1 | | |
| | W5 D4 | | |
| | W6 D1 | | (only take if you are in the third group of the study) |
| | W6 D4 | | (only take if you are in the third group of the study) |

Patient's Signature: _____ Date: _____

Study Team will complete this section:

5. Date patient started protocol treatment _____
6. Date patient was removed from study _____
7. Patient's planned daily dose _____
8. Total number of pills taken this month _____

Physician/Nurse Practitioner/Nurse's Signature: _____

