3.1.5 Dose Escalation

This study will use a 3+3 design, with 3-6 patients enrolled per dose level to define maximum tolerated dose (MTD). The MTD is the dose level at which no more than 1 of up to 6 patients experience DLT within 1 month of completion of treatment, and the dose below that at which at least 2 (of ≤6) patients have DLT as a result of selinexor/RT/temozolomide. If a patient did not experience DLT and did not finish treatment, he or she will not be evaluable for toxicity and will be replaced in the dose level. Enrollment to a dose level would stop if 2 or more patients had a DLT.

The number of patients may be increased to 9 total patients at the MTD (provided no DLT) with a maximum of 21 evaluable patients enrolled and the minimum evaluable patients required will be 15. The once weekly dosing schedule was based on the results of the KCP-330-004 study Arm D. The twice weekly dose of 60mg is from KCP-330-004 Arm C.

| Dose Escalation Schedule of Selinexor | |
|--|--|
| Dose Level | |
| Level -1 | 80 mg on weeks 1, 4 |
| Level 1 | 80 mg on weeks 1, 2, 4, 5 |
| Level 2 | 60 mg twice a week on weeks 1, 2, 4, 5 |
| Level 3 | 60 mg twice a week, weeks 1-6 |

All patients will receive 2Gy daily RT plus 75mg/m² temozolomide.

Dose escalation will follow the rules outlined in the Table below.

| Number of Patients with DLT at a Given Dose Level | Escalation Decision Rule |
|---|--|
| 0 out of 3 | Enter up to 3 patients at the next dose level |
| ≥ 2 | Dose escalation will be stopped. This dose level will be declared the maximally administered dose (highest dose administered). Up to three (3) additional patients will be entered at the next lowest dose level if only 3 patients were treated previously at that dose. |
| 1 out of 3 | Enter up to 3 more patients at this dose level. 
• If 0 of these 3 patients experience DLT, proceed to the next dose level.• If 1 or more of this group suffer DLT, then dose escalation is stopped, and this dose is declared the maximally administered dose. Up to three (3) additional patients will be entered at the next lowest dose level if only 3 patients were treated previously at that dose. |
| ≤ 1 out of 6 at highest dose level below the maximally administered dose | This is the MTD and is generally the recommended phase 2 dose. At least 6 patients must be entered at the recommended phase 2 dose. |

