3.2 DRUG ADMINISTRATION

3.2.1 Selinexor

At dose level 1, Selinexor will be administered orally at an initial dose of 80 mg. The first dose will be given on day 2 of radiation and will thereafter be administered weekly on the second day of weekly radiation on weeks 1, 2, 4, and 5. If dose level 1 is tolerated, the Selinexor dose will be escalated to 60 mg twice a week on weeks 1, 2, 4, 5 given on Monday and Thursday. The third and final dose level will be 60 mg administered twice a week (on Monday and Thursday of radiation) for 6 weeks.

Prophylactic concomitant treatments with a 5-HT3 antagonist and olanzapine may be administered per section [4](#).

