3.2.2.1 CCR self – administered study drugs policy

All oral self-administered study drug will be properly accounted for, handled, and disposed in accordance with existing federal regulations and principles of Good Clinical Practice. All oral study drugs will be recorded in the patient diary found in [Appendix H](#) or [Appendix I](#). This will be used as a memory aide for subjects. The clinical research team will maintain the primary source record. Subjects should be asked to bring the diary as well as unused study drug and empty containers with them at each study visit. If a subject goes off study while at home, the research nurse will ensure and document the return of the unused oral study drug from the participant. Unused study drug will be disposed and destroyed per CC pharmacy SOPs.

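### The twice-weekly selinexor diary (Appendix I) restricts week 6 but not week 3 to the third group, so it shows two doses that Level 2 does not schedule; the weekly diary (Appendix H) has a similar but less certain mismatch

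*Combined protocol and SAP*

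**What the plan says.** The dosing table in section 3.1.5 gives Level 1 as "80 mg on weeks 1, 2, 4, 5", Level 2 as "60 mg twice a week on weeks 1, 2, 4, 5" and Level 3 as "60 mg twice a week, weeks 1-6". Level -1, the fallback, is 80 mg in weeks 1 and 4 only. Section 3.2.1 agrees for Levels 1 to 3. It puts the weekly dose on the second radiation day and the twice-weekly doses on Monday and Thursday, and it adds: "The third and final dose level will be 60 mg administered twice a week (on Monday and Thursday of radiation) for 6 weeks".

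Patients record their doses on one of two forms.

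- **Appendix I (twice weekly, Levels 2 and 3)** has rows for days 1 and 4 of weeks 1 to 6. The comments cells of W6 D1 and W6 D4 read "only take if you are in the third group of the study". Those of W3 D1 and W3 D4 are blank.
- **Appendix H (weekly, Levels -1 and 1)** has one day 2 row for each of weeks 1 to 5, including W3 D2, with no restriction on any row. Its instruction reads "You will take selinexor tablets on the second day of radiation and by mouth once a week".

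Both forms also say "Please ask your doctor what dose you will be getting and how often you will get it". Section 3.2.2.1 describes the diary as a memory aid and states: "The clinical research team will maintain the primary source record".

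**The concern.** The schedule is clear, and the patient forms do not reproduce it. Levels 2 and 3 share the same dose and the same days, and differ only in whether weeks 3 and 6 are dosed. Appendix I draws that distinction for week 6 and omits it for week 3. Once some rows are limited to the third group, the natural reading is that the unmarked rows apply to everyone.

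The drug is investigational and self-administered, and dose levels here are defined partly by which weeks are dosed. A Level 2 patient who dosed in week 3 would receive part of what separates Level 3 from Level 2, in a cohort of three to six where two DLTs stop enrollment to the level. Clear written cues matter more than usual because section 12.3 notes that cognitive incapacity is common in this population.

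**Working it through.** The plan states no figure on this point, so the check compares scheduled doses with the diary rows left open to each level.

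**Inputs.** Weeks and doses per level: sections 3.1.5 and 3.2.1. Diary rows: Appendices H and I. Tablet strength, 20 mg: section 14.1.3.

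**Formulas.** Scheduled dose = weeks dosed × doses per week × mg per dose. Diary total = open rows × mg per dose. Surplus = diary total − scheduled dose.

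| Level | Form | Scheduled | Open rows | Surplus |
|---|---|---|---|---|
| -1 | H | 2 × 80 = 160 mg | 5 × 80 = 400 mg | 3 rows (W2, W3, W5), 240 mg |
| 1 | H | 4 × 80 = 320 mg | 5 × 80 = 400 mg | 1 row (W3), 80 mg |
| 2 | I | 8 × 60 = 480 mg | 10 × 60 = 600 mg | 2 rows (W3 D1, W3 D4), 120 mg |
| 3 | I | 12 × 60 = 720 mg | 12 × 60 = 720 mg | none |

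**Relative size.** Level 1: 80/320 = 25%. Level 2: 120/480 = 25%. Level -1: 240/160 = 150%. In tablets, the ceilings are 80/20 = 4 at Level 1, 120/20 = 6 at Level 2 and 240/20 = 12 at Level -1.

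**What separates Levels 2 and 3 on the form.** 12 − 8 = 4 rows: W3 D1, W3 D4, W6 D1 and W6 D4. Two carry the restriction and two do not. The 120 mg surplus at Level 2 is half of the 720 − 480 = 240 mg gap between the levels.

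**Effect on the design figures.** With p the DLT rate and q = 1 − p, the probability of escalating under the section 3.1.5 rules is q³ + 3pq² × q³. For p = 10% to 60% this gives .906, .709, .494, .309, .172 and .082, which agrees with the table in section 10.2 after rounding. The diary rows do not enter this calculation.

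**The case against.** The strongest reply is that the forms do not govern dosing. The schedule does, and it is consistent across two sections. Both diaries send the patient to the doctor for dose and frequency. Patients attend on site each weekday for radiation (sections 3.1.1 and 3.6.1) and have a weekly on-treatment visit (section 3.5). The NIH pharmacy controls dispensing (14.1.1), the team discusses each patient weekly (7.4.1), and non-compliance is documented as a deviation (8.8). An extra dose also needs surplus tablets in the patient's hands, and the documents give no dispensing quantities. All of this stands. It makes an extra dose unlikely and probably detectable, but it does not make the forms agree with the schedule.

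A second reply is aimed at Appendix H. A blank row is a place to record, not an order to take a dose. Section 3.2.1 itself describes the correct Level 1 schedule as weekly, so the form's once-a-week instruction may be the same shorthand. The table as extracted also has a stray empty row and column, so a note or shading could have been lost. This stands in part, and it is why Appendix H is held with less confidence. It carries less weight for Appendix I, where the week 6 restriction was read as text and the week 3 cells beside it are blank.

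A reader might go further and infer that patients at Levels 1 or 2 took week 3 doses, that DLTs were therefore attributed to the wrong level, or that the MTD is compromised. The documents do not support this. They contain no record of such a dose, and the controls above mean that one should be known when a DLT is assessed.

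**Conclusion.** The mismatch is real and minor. Appendix I is wrong for Level 2 on its face, with high confidence: 0 to 120 mg of unscheduled selinexor on top of 480 mg. Appendix H is a softer case: 0 to 80 mg on top of 320 mg at Level 1 and, only if Level -1 is opened, 0 to 240 mg on top of 160 mg. The upper ends assume that the patient follows the form literally, has the extra tablets and is not corrected by staff. The lower end of zero is the more likely outcome. The DLT definition, the escalation rules, the MTD definition and the sample size do not change. What is at risk is a wrong dosing cue to patients and, if one were followed unnoticed, a less clean attribution of toxicity to dose level.

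**What to change.** - **Appendix I:** add "only take if you are in the third group of the study" to W3 D1 and W3 D4.
- **Appendix H:** delete W3 D2, and mark W2 D2 and W5 D2 as not taken at Level -1. Deleting the week 3 row alone would leave the form wrong for that level.
- **Alternative:** issue one diary per dose level, which settles all four levels at once.
- **Check:** review returned diaries and unused drug for week 3 doses at Levels 1 and 2, and report any as deviations alongside the DLT data.

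With these changes the open rows equal the schedule: 2, 4, 8 and 12 doses at Levels -1, 1, 2 and 3.

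The cost is two replacement participant forms. Under the Statement of Compliance, participant materials go to the IRB and amendments need its approval before they are implemented. The check uses diaries, unused drug and containers that section 3.2.2.1 already asks patients to bring to each visit. No extra patients are needed, and the design does not change.
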